Aerobic exercise is often prescribed to reduce CVD risks; however, controversy exists regarding the optimal exercise prescription for preserving or restoring endothelial function in older adults. Moderate-intensity aerobic exercise ameliorates endothelial dysfunction in older men, but the data in postmenopausal women are inconsistent, with most studies showing no effect (reviewed in Seals et al⁵). The mechanisms underlying these sex disparities in healthy aging are unknown. A recently introduced theory of exercise-induced hormesis proposes that an acute exercise bout that generates an optimal level of stress can stimulate adaptations to increase resistance against subsequent stressors; if the exercise-induced stress does not reach this threshold, then adaptation will not occur. Consistent with this theory, higher exercise intensity is thought to be required to induce chronic endothelial adaptations in postmenopausal women, but this has not been

investigated. High intensity interval training (HIIT) is receiving considerable attention as an innovative strategy for cardiac rehabilitation, but data in sedentary aging are limited^{6, 7}. HIIT involves short periods of vigorous exercise, mainly “uphill” treadmill walking, interspersed by periods of moderate-intensity exercise. However, weight-bearing HIIT is often problematic in older adults due to musculoskeletal issues. *We have recently developed a novel alternative by adapting HIIT to a non-weight-bearing all-extremity (NWA) ergometer; our innovative NWA-HIIT allows compensation for lower extremity weakness/fatigue.* We have established in sedentary older adults that NWA-HIIT is feasible, well-tolerated and safe⁸. Our preliminary data suggest that 8-week NWA-HIIT improves endothelial function in older men, but not in postmenopausal women. Our preliminary studies also indicate substantial sex differences in acute endothelial responsiveness to HIIT; there is a transient attenuation in endothelial function in older men following an acute bout of HIIT, but this is absent in postmenopausal women. We postulate that in men, NWA-HIIT presents an optimal challenge to endothelial homeostasis thereby initiating chronic adaptive responses; in contrast, the stimulus is inadequate for chronic adaptations in postmenopausal women. *Accordingly, acute responses to exercise may provide keys to understanding sex-related differences in long-term endothelial adaptive responses to exercise.*

[figure not shown]

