[figure not shown]
Our overarching hypothesis is that acute and chronic endothelial responsiveness to aerobic exercise is influenced by sex in healthy aging and acute endothelial responses will be predictive of chronic endothelial adaptations. Our experimental model of acute and chronic responses to NWA-HIIT presents a unique tool to test this hypothesis and explore the underlying mechanisms in healthy sedentary older adults. *Our translational approach will examine, for the first time, sex differences in endothelial responses to exercise at multiple levels spanning from the molecular and cellular to the organism level. Identifying the defective adaptive pathways in women may lead to novel therapeutic targets.*

5. Specific Aims

1. To study sex differences in chronic endothelial adaptations to aerobic exercise
2. To study sex differences in acute endothelial responses to aerobic exercise and if acute endothelial responses are predictive of chronic endothelial adaptations.

6. Research Plan

Study design and timing of measures. An equal number of older men and postmenopausal women will be enrolled in this study and the same subjects will complete Aims 1 and 2. For Aim 1, subjects will complete 8-week NWA-HIIT preceded by an 8-week control period of normal lifestyle. Therefore, each subject will serve as his/her own control and the control period of normal lifestyle will also allow determination of potential changes due to measurement error. FMD and other measures associated with Aim 1 will be assessed at baseline, and after the 8-week control and 8-week NWA-HIIT (**Diagram 1**). FMD and other measures associated with Aim 2 will be assessed at pre-exercise, at the end of a single session of NWA-HIIT, and 1-hr and 24-hrs post-exercise (**Diagram 2**) in the untrained and trained state (**Diagram 1**). Measures in the trained state for Aim 2 will be completed 72-96 hours after the last chronic exercise session.

Study procedures will be performed at the Integrative Cardiovascular Physiology Laboratory, Center for Exercise Science, University of Florida.

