Sample Size, Statistical Analyses, and Anticipated Results

Sample size justification. For power analyses, we set $\alpha=0.05$ and $\beta=0.80$ and used the smallest effect size (ES) based on our preliminary data on FMD, which is our primary outcome. To detect significant sex differences in acute/chronic FMD responses, we will need 11 men and 11 women (ES=1.57 for acute and 1.28 for chronic response). To detect

significant acute and chronic changes in FMD in response to NWA-HIIT in older men we will need 10 men (ES=1.02 for acute and 3.87 for chronic response). We anticipate we will need to consent and screen 165 research participants to meet the study inclusion criteria and obtain complete datasets in 11 men and 11 women.

Statistical analyses. Our primary outcome will be FMD. For both Aim 1 and 2, we will use mixed factorial ANOVA. Post hoc and multiple tests will be corrected using the Bonferroni adjustment. Secondary analyses will be performed using ANCOVA to account for influence of potential confounders. Exploratory analysis will evaluate the mechanisms by which exercise influences FMD and stimulate future mechanistic studies. Using linear regression, we will examine whether responses to acute NWA-HIIT are correlated with responses to chronic 8-week NWA-HIIT. Analysis of the RNA sequencing data will be conducted by the ICBR bioinformatics staff.

HUMAN SUBJECTS

Human Subject Characteristics

Subjects will be sedentary men and postmenopausal women recruited from the community using advertisements. Subjects will be screened by our experienced study clinicians with oversight by our cardiologist ([name]) according to the study inclusion/exclusion criteria based on the medical history, physical examination, general blood tests and diagnostic maximal exercise test.

Inclusion criteria

- adults able to give consent
- men and women
- women must be postmenopausal (either natural or surgical)
- 60 to 79 years of age

Exclusion criteria

- any relevant cardiovascular diseases (e.g., history of coronary artery bypass surgery or angioplasty, or heart failure, myocardial infarction, angina pectoris, peripheral arterial disease)
- myocardial ischemia during maximal graded exercise test
- major chronic clinical disease (e.g., diabetes, renal or hepatic disease or infection with hepatitis B, C, or HIV)
- seizures, or other relevant on-going or recurrent illness
- recent (within 3 months) or recurrent hospitalizations
- systolic blood pressure <100mmHg

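### The regression of chronic on acute FMD response names no sex term; fitted across both sexes, it could present the sex contrast as individual-level prediction

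*Combined protocol and SAP*

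**What the plan says.** Section 5 (Specific Aims) makes prediction the second half of Aim 2, and the overarching hypothesis at the end of section 4 states that "acute endothelial responses will be predictive of chronic endothelial adaptations". The analysis for this is one sentence under Statistical analyses: "Using linear regression, we will examine whether responses to acute NWA-HIIT are correlated with responses to chronic 8-week NWA-HIIT". It gives no covariate, no by-sex fit and no interaction, and does not say which subjects enter the fit.

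The sentence just before it reads "Exploratory analysis will evaluate the mechanisms by which exercise influences FMD and stimulate future mechanistic studies". The same paragraph plans secondary ANCOVAs for confounders that it does not name, and does not link them to this regression. It also has a general multiplicity rule: "Post hoc and multiple tests will be corrected using the Bonferroni adjustment".

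The plan expects sex to shift both variables. On the acute side, the Background section reports that "there is a transient attenuation in endothelial function in older men following an acute bout of HIIT, but this is absent in postmenopausal women". On the chronic side, it reports improvement over 8 weeks in men and none in women. The sample size rests on these contrasts: "we will need 11 men and 11 women (ES=1.57 for acute and 1.28 for chronic response".

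**The concern.** Sex is the design factor, and it is expected to move both the predictor and the outcome. Men should form a cluster with an acute fall and a chronic gain; women should sit near zero on both. A single line through two such clusters slopes from one to the other, whether or not the men with the larger acute fall are the men with the larger chronic gain.

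The slope would be negative (attenuation goes with improvement), which is the direction that the hypothesis predicts. A positive result could then be reported as meeting the predictive half of Aim 2 while only restating the two sex differences that the factorial ANOVA already tests.

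**Working it through.** **Inputs.** 11 men and 11 women; standardised sex differences 1.57 (acute) and 1.28 (chronic); alpha 0.05, taken as two-sided; the planned 0.80 read as power. All are from Sample size justification. The directions are from Background. The within-sex correlation rho is not given; it is set to 0 for the main case and varied below.

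**Step 1: what the effect sizes are.** A two-sample t test at d = 1.28 has power 0.77 with 10 per sex and 0.81 with 11, which reproduces the plan's 11. A one-sample t test on change at 1.02 has power 0.76 with 9 men and 0.82 with 10, which reproduces the plan's 10. So 1.57 and 1.28 behave as standardised sex differences in response.

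**Step 2: correlation created by sex alone.** For two equal groups with unit SD, differences −d1 and +d2, and within-sex correlation rho:

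r = (rho − d1·d2/4) / √[(1 + d1²/4)(1 + d2²/4)]

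At the planning values with rho = 0: d1·d2/4 = 1.57 × 1.28/4 = 0.502; the two variance terms are 1.616 and 1.410, and the root of their product is 1.509. So r = −0.502/1.509 = −0.33.

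**Step 3: rejection rates.** Simulation of 200,000 trials per case, 11 per sex, normal responses, equal SDs, rho = 0:

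| True sex differences (acute/chronic) | Pooled r | p<0.05, no sex term | p<0.05, sex in model |
|---|---|---|---|
| 1.57/1.28 | −0.33 | 35% | 5% |
| 1.0/1.0 | −0.20 | 15% | 5% |
| 0.8/0.8 | −0.14 | 9% | 5% |
| 0.5/0.5 | −0.06 | 6% | 5% |

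At the planning values almost all rejections are in the negative direction.

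**Step 4: the opposite error.** With a within-sex correlation of +0.6 and the planning sex differences, the pooled r is (0.6 − 0.502)/1.509 = 0.06. The fit without sex rejects in about 2% of trials; with sex it rejects in about 86%.

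**Step 5: unequal SDs.** At the planning values and rho = 0, with a 2:1 SD ratio on both axes (same sex larger / opposite sexes larger), the fit without sex rejects in 38% / 34%. With sex, ordinary least squares (OLS) rejects in 9% / 2% and HC3 in 6% / 3%.

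A more extreme case assumes that 3.87 is the men's mean change over its SD, that women do not change, and that 1.28 uses the pooled SD. The chronic SD ratio is then √(2 × (3.87/1.28)² − 1) = 4.16. With acute SD ratios of 0.5, 1 and 2, the fit without sex rejects in 33%, 36–37% and 39%; OLS with sex in 0.7%, 5.0% and 11.5%; HC3 in 1.2%, 2.8% and 5.7%.

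**Step 6: power of the sex-adjusted slope (equal SDs).** About 26% at |rho| = 0.3 and 67% at 0.5 (HC3 23% and 59%); 80% needs about 0.57. If prediction holds only in men (rho −0.5, women 0), the common slope has about 20% power and the interaction about 19%.

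**The case against.** The strongest reply is that the plan never says the sexes are pooled. A reader might infer that a two-variable fit to all 22 subjects is the planned analysis. The text does not establish this, since a by-sex or adjusted fit is equally compatible with it. What stands is that nothing excludes pooling, and the rates above are conditional on it.

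Second, the documents speak of correlation and prediction without saying within sex, and Background suggests that acute responses may help to explain the sex difference itself. On that view the pooled correlation of −0.33 is real, and 35% is a false-positive rate only against a within-sex null that the plan does not state. That is fair. But a pooled slope alone cannot distinguish this explanation from a plain sex difference in each response, so both slopes are needed.

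Third, the position of the sentence suggests an exploratory analysis. It may be one, but the question is named in Aim 2 and in the hypothesis, and an exploratory label does not change what the slope measures.

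Fourth, acute FMD is measured "at the end of a single session of NWA-HIIT, and 1-hr and 24-hrs post-exercise", and a reader might infer uncorrected testing of three time points. The Bonferroni sentence appears to exclude that.

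**Conclusion.** The point holds as a gap with a cheap and better alternative. If fitted across both sexes without a sex term, the regression has about a 35% chance of a significant slope at the plan's own effect sizes with no within-sex association. That falls to 6% if the true sex differences are 0.5 on both axes. These figures assume normal responses and equal SDs; at the planning values the 35% moves only to 33–39% across the SD ratios tried.

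Two further inferences should be resisted. Adding sex does not guarantee exactly 5%: that holds for equal SDs, and OLS ranged from 0.7% to 11.5% in the most extreme case, which rests on several assumptions. Nor does this point show that post-training FMD is missing. The Visit 10 listing omits the blood vessel tests although the Blood vessel tests section calls for them after training, but the list may be incomplete and Visit 12a includes a pre-exercise measurement. That mismatch is a separate matter to reconcile.

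The primary mixed factorial ANOVA is unaffected.

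**What to change.** Replace the sentence with text to this effect:

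*Chronic FMD change will be regressed on untrained-state acute FMD change with sex as a covariate. Any claim of individual-level prediction will rest on the sex-adjusted slope, with heteroscedasticity-robust (HC3) standard errors reported. The pooled slope, the slope within each sex and the sex-by-acute interaction will be reported descriptively with 95% confidence intervals. If more than one acute time point is tested, the Bonferroni rule of this plan applies.*

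Add one sentence stating whether the analysis is confirmatory for Aim 2 or exploratory.

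The cost is a few sentences, no new data and one residual degree of freedom (20 to 19). Power is limited with 22 subjects, and a common slope averages the sexes if prediction exists only in men. A null result should therefore be given with its confidence interval and not read as absence of prediction.

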- Endothelial cell collection and analysis. We have the experience, resources, and access to experts to support the proposed endothelial cell measures. The proposed study will lay the foundation upon which we will base future studies focusing on dissecting *in vivo* the sex-specific effect of exercise on mechanisms of endothelial dysfunction. The procedures for studying endothelial cells have been described in detail by Colombo et al¹⁶⁻¹⁸, and by our group^{11, 19-22}. A clinician on our team from the Pulmonary and Critical Care Division, [name], who has extensive experience with intra-arterial catheterizations (~1500 procedures over 15 years) will perform the procedure. He will place a standard 20 gauge arterial catheter with no sheath at the radial artery guided by ultrasonography after numbing the area with local lidocaine injection. No vasodilators will be used. Once the catheter is secure, four small (0.018-inch diameter) sterile J-shaped guidewires will be sequentially advanced (~4 inches) through the radial arterial catheter and retracted to collect a small number of endothelial cells. Following the cell collection and blood draw, the catheter will be removed and hemostasis will be achieved by manual compression of the site. The physician will monitor bleeding at 5, 10 and 15 minutes after removal of the catheter to assure hemostasis and no hematoma formation. Subjects will not be on anticoagulants, therefore normal coagulation time is anticipated. Cells will be recovered by rinsing the wires and centrifugation. Endothelial cell protein levels of key factors associated with oxidative stress, inflammation, and endothelial function and sex hormone receptors will be examined using immunostaining. Detailed procedures for immunofluorescence staining and analysis have been described previously by our

group ^{11, 19-22}. Endothelial cells will also be analyzed using RNA sequencing to identify new pathways that lead to sex differences in endothelial responses to exercise in older adults.

- To investigate the chronic effects of HIIT, cells will be collected and analyzed: 1) at baseline; 2) after 8 weeks of normal lifestyle; and 3) after 8 weeks of exercise training.

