- Nitroglycerin test- The oral administration of nitroglycerin (0.4 mg sublingual tablet) is expected to cause a small transient decrease in arterial blood pressure. The subject may experience increased heart rate, lightheadedness, tingling on the tongue and in the arms and legs, light headache, and at the extreme, fainting. In rare cases heart rate may decrease in response to the nitroglycerin pill which can also cause fainting. The dose of nitroglycerin used is considered safe and is commonly used in patient populations to relieve angina. With any drug used in testing, there is a small risk of an unforeseen life-threatening allergic reaction. The on-site study clinician will confirm that there are no contraindications for nitroglycerin administration (e.g., systolic blood pressure <100 mmHg, phosphodiesterase inhibitors including Sildenafil) before administering the drug and will monitor the subject until ready to be released.

Protection Against Risks

In general, risks will be minimized by:

- allowing only individuals who meet the inclusion criteria to participate
- screening for contraindications for nitroglycerin administration, maximal graded exercise testing or intra-arterial catheter placement
- providing clinical supervision, including ECG and blood pressure monitoring, for the maximal graded exercise tests and nitroglycerin administration
- ensuring constant personal monitoring of each experimental session by the investigators
- using only safe, well-established procedures, and having only qualified and experienced personnel perform the procedures
- following UF guidelines for reducing the risk of COVID-19
- having available emergency equipment/medications and well-planned emergency procedures
- providing complete confidentiality

Risks associated with COVID-19: Risks related to COVID-19 will be mitigated by strictly following UF COVID-19 safety guidelines and the advice of [name], a Co-Investigator and experienced clinician at the UF Health Division of Pulmonary and Critical Care. These include:

- Limiting the number of people in a room and social distancing whenever possible.
- Frequently sanitizing laboratory surfaces and hands.
- Study personnel wearing KN95 masks and shields, disposable gowns and gloves and participants wearing a surgical mask.

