- Upon arrival at the Center for Exercise Science for a scheduled visit, participants will be screened for history and symptoms of COVID-19 and body temperature will be taken using a contactless forehead thermometer prior to exiting their car. If they answer yes to any of the screening questions and/or their temperature is greater than 100.4 degrees, then they will need to reschedule the visit. Participants will be given a surgical mask and a 2 oz. bottle of hand sanitizer. They will be asked to wear the mask and use the hand sanitizer prior to entering the building and frequently sanitize their hands during the visit and social distance whenever possible.
- During the pandemic, participants will complete a COVID-19 test 3-5 days prior to VO₂max testing and only those who are confirmed negative will proceed to complete the VO₂max test. The COVID-19 test will be prescribed as long as [name] deems it necessary and will be paid by the study.
- Exercise sessions will be performed at home and exercise supervision will be conducted remotely live via UF Zoom using a wearable device which provides real-time heart rate monitoring.

Specific risks associated with nitroglycerin: Risks related to nitroglycerin administration will be minimized by providing adequate clinical supervision and by taking the following safety precautions. An intravenous catheter will be inserted in a peripheral vein prior to nitroglycerin administration, in case the effect of nitroglycerin necessitates the administration of fluids or medication. ECG will be monitored continuously. Blood pressure will be monitored prior to nitroglycerin administration and post-administration as frequently as deemed necessary. For individuals whose systolic blood pressure is <100 mmHg, nitroglycerin will not be administered. Subjects will remain in bed for 30 minutes after nitroglycerin administration to allow blood pressure to return to baseline before ambulating. Nitroglycerin has been administered safely in our laboratory for more than 10 years, and in other laboratories, and clinical situations worldwide.

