Risks associated with intra-arterial catheter and cell collection: Risks related to intra-arterial catheter insertion and cell collection will be minimized by having an experienced clinician from the Pulmonary and Critical Care Division, [name], perform the procedure. [name] will use ultrasound imaging to guide the cannulation to avoid injury to nerves and surrounding structures. Subjects will be screened for contraindications including absent pulse at the location of the artery, history of Raynaud's Syndrome, insufficient collateral perfusion based on Allen test, coagulopathy, recent use of thrombolytic, anticoagulant or antiplatelet drugs, and partial or full thickness burns over the proposed cannulation site. Up to two attempts to insert the arterial catheter will be performed; attempts will be aborted if any complications are expected. [name] will monitor the patient until the arterial line procedure and cell collection are completed and no complications are noted.

Specific risks and complications will be mitigated and managed as follows:

- a. Radial Artery Spasm (RAS)
 - i. Subjects will be monitored for RAS clinically by physician inserting arterial catheter
 - ii. Initial management:
 1. Subjects scheduled to receive nitroglycerin 0.4 mg sublingual (as per study protocol to assess endothelium-independent dilation) will receive the dose of nitroglycerin as per study protocol and RAS will be reevaluated (at 10-min intervals up to 30 min). If no improvement, then escalation to higher level of care will be initiated.
 2. Subjects not scheduled to receive nitroglycerin will be monitored for severity of RAS. If moderate or severe by clinical judgement, then the patient will receive a single dose of nitroglycerin 0.4 mg sublingual and RAS will be reevaluated (at 10-min intervals up to 30 min). If no improvement, then escalation to higher level of care will be initiated.
- b. Thrombosis
 - i. Mitigation of risk:
 1. Cancel procedure if subject has history (or present during evaluation) of Raynaud's phenomenon
 2. Catheter will stay inserted for less than 5 min
 3. No use of large bore catheters, only 20G or smaller

4. No insertion if patient has low cardiac output (by history)
5. No insertion if patient has history of severe peripheral artery disease
6. No insertion if blood vessel is considered too small for cannulation

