- ii. Initial management: If moderate or severe by clinical judgement, then the patient will receive a single dose of nitroglycerin 0.4 mg sublingual and RAS associated with thrombosis will be reevaluated (at 10-min intervals up to 30 min). If no improvement, then escalation to higher level of care will be initiated.

- c. Dissection, pseudoaneurysm, AV fistula
 - i. Mitigation of risk by using procedures described above and
 1. Continuous clinical monitoring at 10-min intervals up to 30 min.
 2. Local pressure to control bleeding and hematoma
 3. If present and no improvement with initial local pressure, then escalation to higher level of care will be initiated.
- d. Infection
 - i. Mitigation of risk:
 1. All sterile insertion as per usual guidelines. Use of mask, caps, gowns, sterile gloves, and chlorhexidine (or equivalent if patient allergic) to prepare the skin.
 2. Catheter will be inserted for less than 5 minutes.
- e. Blood loss
 - i. Mitigation of risk:
 1. No arterial puncture will be attempted in any subject with systemic anticoagulation.
 - ii. Initial management:
 1. Bleeding will be controlled by local pressure; monitoring at 5, 10, and 15 min after removal of arterial catheter. If bleeding persists continuous pressure and evaluation at 10-minute intervals up to 30 min.
 2. If bleeding present and no improvement with initial local pressure, then escalation to higher level of care will be initiated.
- f. Neuropathy
 - i. Mitigation of risk:
 1. Use of ultrasound guided technique to avoid nerve injury.
 2. Abort procedure if producing pain or neurological injury.
 - ii. Initial management:
 1. If severe neurological injury noticed, then escalation to higher level of care will be initiated.

Procedure for escalation of care after initial control in research laboratory:

Local initial first aid, including pressure to stop bleeding and vital signs monitoring. The patient will be transferred to University of Florida Hospital for further evaluation and care if complications arise. If emergent we will contact 911 for immediate support and transport. We will immediately refer patient to University of Florida/Shands Medical Center for any complications for further evaluation and therapy.

Risks associated with exercise training:

In general, risks related to exercise training will be minimized by:

- adhering to the exercise training guidelines published by the American Heart Association and the American College of Sports Medicine

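### Do the catheter-complication rules order nitroglycerin for participants from whom the protocol withholds it?

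*Combined protocol and SAP*

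**What the plan says.** Three directives under the intra-arterial catheter heading of Section 7 involve nitroglycerin.

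- **Spasm, a.ii.1**, for participants with a scheduled test dose: they "will receive the dose of nitroglycerin as per study protocol and RAS will be reevaluated".
- **Spasm, a.ii.2**, for the others: "Subjects not scheduled to receive nitroglycerin will be monitored for severity of RAS", followed by "If moderate or severe by clinical judgement, then the patient will receive a single dose of nitroglycerin 0.4 mg sublingual".
- **Thrombosis, b.ii**, with no limit on who is covered: if the event is moderate or severe, "the patient will receive a single dose of nitroglycerin 0.4 mg sublingual and RAS associated with thrombosis will be reevaluated".

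Statements on withholding or screening stand earlier in Section 7.

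- The nitroglycerin test bullet has the on-site clinician rule out "contraindications for nitroglycerin administration (e.g., systolic blood pressure <100 mmHg, phosphodiesterase inhibitors including Sildenafil) before administering the drug".
- The general list under Protection Against Risks includes "screening for contraindications for nitroglycerin administration, maximal graded exercise testing or intra-arterial catheter placement".
- The paragraph on specific risks of nitroglycerin says: "For individuals whose systolic blood pressure is <100 mmHg, nitroglycerin will not be administered".

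Systolic pressure below 100 mmHg is also an exclusion criterion; use of phosphodiesterase inhibitors is not. The description of endothelial cell collection adds, about the catheter procedure, "No vasodilators will be used".

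**The concern.** Rules a.ii.2 and b.ii are mandatory in tone and depend on severity alone. The blood-pressure prohibition is equally mandatory. Neither side mentions the other, so a literal reader could find two instructions for one participant and nothing saying which prevails. The contrast with a.ii.1, which does refer back to the study protocol, makes the omission more visible.

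Phosphodiesterase inhibitors leave the widest gap. They are named only in the test bullet, and the later prohibition mentions blood pressure only. The group covered by a.ii.2 is also unclear, because no planned cannulation visit lacks a nitroglycerin test. One possible reading is that it reaches people whose test dose was withheld, some of whom would be the contraindicated ones. Rule b.ii does not say how its dose relates to a test dose at the same visit.

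At stake is the safety of individual participants during an acute complication. No estimate or test is involved.

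**Working it through.** No formula applies and the plan states no figure to reproduce. The check sets the texts side by side and makes three counts.

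**Counts**

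1. Directives without a reference back: a.ii.1 has one; a.ii.2 and b.ii have none. That is 2 of 3.
2. Cannulation visits without a scheduled nitroglycerin test: the visit list puts arterial cannulation at Visits 5, 7 and 10 and the nitroglycerin test at Visits 5, 7 and 10. That is 0 of 3.
3. Planned cannulation visits among completers: (11 men + 11 women) × 3 = 66. This is a minimum, because participants who leave after Visit 5 add to it. The documents give no rate of moderate or severe complications and no rate of visit-day contraindication, so the 66 cannot be turned into an expected number of affected visits.

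**Blood pressure**

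The prohibition stands under a heading about the drug and carries no restriction to the test. An unqualified statement that the drug is not given below a threshold naturally limits later instructions to give it. The exclusion criterion narrows the overlap further, although pressure on a visit day can differ from pressure at screening. Visits 5, 7 and 10 each list a blood pressure measurement.

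**Phosphodiesterase inhibitors**

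The check that names them is in the test bullet, but it is tied to the moment before the drug is given. The general list repeats contraindication screening for nitroglycerin as a protective measure for the whole study. By count 2, the check is due at every visit where one of these complications could arise. The 24-hour questionnaire, listed at the same three visits, asks about medication intake.

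**The spasm branch without a scheduled dose (a.ii.2)**

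By count 2 it matches no planned visit. It reaches a participant whose dose was withheld only if withholding makes that person unscheduled. It is just as natural to say that a listed but withheld test leaves the participant under a.ii.1, which refers back to the protocol. On that reading only b.ii lacks a link in practice.

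**The sentence on vasodilators**

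It stands between placing the catheter and advancing the guidewires, so it describes routine technique. It cannot exclude nitroglycerin from the visit, since the test is scheduled at all three of those visits.

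**Effect on the analysis**

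The planned mixed factorial ANOVA of FMD and the target of 11 men and 11 women do not depend on how these rules are read.

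**The case for a change.** The strongest opposing argument is that screening identifies a contraindication but does not say what happens when a complication rule then calls for a dose. Emergency instructions should be the least ambiguous part of a protocol, and a cross-reference costs only wording. In a.ii.2 and b.ii, escalation is worded as following a lack of improvement after the dose, so those rules offer no separate route for someone who cannot receive it.

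Part of this stands. Precedence is not stated, the population of a.ii.2 is loosely described, and b.ii is silent on a test dose at the same visit. An editor could tidy all three.

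It does not show that the plan is wrong. The text has a general prohibition and a pre-dose check on one side, and instructions that rest on a physician's judgement on the other. These can be read together without contradiction. The escalation paragraph also provides for immediate hospital referral for any complication, which does not depend on a dose having been given. The inserting physician monitors the participant throughout, so the person applying the rule can take the earlier statements into account.

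**Conclusion.** The concern does not call for a change. It identifies a missing cross-reference in 2 of 3 nitroglycerin directives and one branch that matches 0 of 3 planned cannulation visits. These are drafting gaps that the study physician would fill sensibly. They have no bearing on the primary outcome, the error rates or the sample size.

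This rests on two readings: that the blood-pressure prohibition applies to nitroglycerin generally, as it is worded, and that the contraindication check applies before any dose at a cannulation visit. If the investigators intended something else for complication doses, the nitroglycerin and catheter paragraphs of Section 7 would have to be reconciled. That clinical decision is theirs, and this review takes no position on it. The frequency of the situation cannot be estimated from the documents, and the conclusion does not depend on it.
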